## **Protocol deviations**

The number (%) of patients in the FAS with any protocol deviation will be tabulated by deviation category (as specified in the study Edit Check Specification) for the FAS. All protocol deviations will be listed.

In addition to the pre-defined standard PD terms, Novartis has also defined new protocol deviations and the corresponding relationship to the COVID-19 pandemic. The protocol deviations related to the COVID-19 pandemic will be summarized.

## **Analysis sets**

The number (%) of patients in each analysis set (defined in [Section 2.2](#)) will be summarized and listed.

## **2.4 Treatments (study treatment, rescue medication, concomitant therapies, compliance)**

### **2.4.1 Study treatment / compliance**

Duration of exposure, actual duration of exposure, cumulative dose, dose intensity (DI) and actual dose intensity (ADI) will be summarized separately for each single component of study treatment. Duration of exposure will be categorized into time intervals; frequency counts and percentages will be presented for the number(%) of subjects in each interval. The number (%) of subjects who have dose reductions or interruptions, and the reasons will be summarized by treatment group.

Subject level listings of all doses administered on treatment along with dose change reasons will be produced.

The safety set will be used for all summaries and listings of study treatment.

### **Duration of exposure to study treatment**

The duration of exposure to each component (called drug X below) of the study treatment will be derived as follows:

Exposure to drug X = Last unit (date/time) of administration of X – First unit (date/time) of administration of X + (1),

where periods of drug interruption will not be deducted if there is no permanent treatment discontinuation following. If the unit is the date, then plus 1; if the unit is the hour, then transfer the exposure duration to days and plus 1 when there are residual hours.

The actual duration of exposure defines as the sum of periods where the dose exposure is non-zero.

Duration of exposure and actual duration of exposure to study treatment will be summarized for each of the study treatment components separately, using descriptive statistics (mean, standard deviation etc). For eltrombopag, the number and percentage of time on study treatment (< 3 months, 3 months to 6 months, > 6 months) will be presented. For CsA, the number and percentage of time on study treatment (< 3 months, 3 months to 6 months, > 6 months to 12

months, > 12 months to 18 months, > 18 months to 24 months) will be presented. A listing of data on subject exposure to study treatment will also be produced.

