6.1.1.2 Rabbit anti-thymocyte globulin (r-ATG)

Usually, r-ATG (Thymoglobuline[®]) will be administered at a dose of 2.5 to 3.5 mg/Kg/day on Days 1 to 5 as a slow intravenous infusion per local practice. The exact dose of r-ATG should be decided at the discretion of the investigator but should be within the above range.

Premedication with corticosteroids, acetaminophen, and/or an antihistamine 1 hour prior to each infusion of r-ATG is recommended and may reduce the incidence and intensity of infusion-associated reactions (detailed in [Section 6.2.1](#)). For the treatment for anaphylaxis and infusion-associated reactions, local label should be followed.

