Eltrombopag dose may be interrupted when clinically indicated at the discretion of the investigator. Interruptions will be reported. For participants who meet any toxicity criteria (see [Section 6.5.1](#)) or who do not tolerate the protocol-specified dosing schedule, the investigator will follow the guideline on dose modification and/or discontinuation presented in [Section 6.5.1](#).

Participants in whom the treatment is assessed as effective at Week 26 may continue treatment with eltrombopag and CsA after Week 26 (in the extension part of the study). Eltrombopag will be provided for the participants who entered the extension part and are considered to require continued treatment up to Week 52. The daily dose of eltrombopag in extension part is shown in [Table 6-3](#) and [Table 6-4](#).

R-ATG

R-ATG will be administered intravenously on Days 1-5. Dosing of r-ATG is defined in [Section 6.1.1.2](#).

Administer r-ATG under strict medical supervision in a hospital setting, and carefully monitor participants during the infusion. The infusion time may vary based on the participant and circumstances. Administer the first dose of r-ATG over a minimum of 6 hours; administer doses on subsequent days over at least 4 hours.

Premedication with corticosteroids, acetaminophen, and/or an antihistamine 1 hour prior to each infusion of r-ATG is recommended and may reduce the incidence and intensity of infusion associated reactions. Prior to the administration of r-ATG, a daily threshold (pre-transfusion) platelet count of $20 \times 10^9/L$ should be used for the duration of the r-ATG course.

Instructions for reconstitution, dilution and infusion from the local label should be followed strictly.

CsA

CsA will be administered orally, every 12 hours. Participants will be instructed to take CsA at the same time each day. Dosing of CsA is described in [Section 6.1.1.3](#).

CsA will be supplied as soft-gelatin capsules or as an oral solution. Switching from the soft-gelatin capsules to the oral solution should be performed with caution and under close physician supervision. The introduction of the new formulation must be made with monitoring of blood levels of CsA to ensure that pre-conversion levels are attained.

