## Document History – Changes compared to previous final version of SAP

Date	Time point	Changes	Section and title impacted (Current)
15-Sep-2020	Prior to FPFV	N/A - First version	NA
1-Jul-2022	Prior to DBL	Update the definition of on-treatment period and post-treatment period according to protocol changes; Update the windows for multiple assessments	Section 2.1.1
		Remove the race subgroup analysis in efficacy, safety and PK; Update the China Mainland/Japan specific subgroup analysis	Section 2.2.1
		Update the definition of duration of exposure with consideration of using hours as unit time for rATG; Add the definition and the corresponding statistical analysis of actual duration of exposure	Section 2.4.1
		Add the definition and the corresponding statistical analysis of actual dose intensity; Remove the planned dose intensity and relative dose intensity	Section 2.4.1
		Remove the summary analysis and the corresponding table for concomitant medications that have the potential to impact efficacy results	Section 2.4.2
		Add the supplementary analysis section to specifically describe the CR response that is derived programmatically using laboratory results	Section 2.5.1; Section 2.5.4
		Update the definition of the relapse; Add the definition and corresponding statistical analysis for below-listed item: Time to response; Maximum duration of Platelet and RBC transfusion free;	Section 2.7

Date	Time point	Changes	Section and title impacted (Current)
		Proportion of subjects with transfusion decrease; Changes in platelet count, hemoglobin and neutrophil count	
		Specify that the CTC grade $\geq 3$ adverse events will be summarized for AEs by SOC and PT	Section 2.8.1
		Add the sub-items for ALT and AST	Section 2.8.3
		Remove the percentage summary table and the shifted table for ECG Findings	Section 2.8.4.1
		Update PD and PK/PD analyses	Section 2.10
		Update the definition of the cytogenetic abnormalities and clonal evolution observed during the study; Remove the time to clonal evolution	Section 2.12
		Add the imputation rule of end dates, when missing component is the hour for rATG	Section 5.1.2

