**Table 5-2      Imputation of end dates (AE, CM)**

Missing Element	Rule (*=last treatment date plus 30 days not > (death date, cut-off date, withdrawal of consent date))
day, month, and year	

• Completely missing end dates (incl. ongoing events) will be imputed by the end date of the on-treatment period*

day, month	

• If partial end date contains year only, set end date = earliest of 31DecYYYY or end date of the on-treatment period *

day	

• If partial end date contains month and year, set end date = earliest of last day of the month or end date of the on-treatment period*

hour	

• For rATG end dates only, if partial end time contains no time, then set the time to 00:00.

Any AEs and ConMeds with partial/missing dates will be displayed as such in the data listings.

Any AEs and ConMeds which are continuing as per data cut-off will be shown as 'ongoing' rather than the end date provided.

The above imputations are only used for analyses of time to and duration of AEs and concomitant medications.

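### The hour-based r-ATG exposure rule counts 24-hour blocks, not dosing days, so some complete Day 1–5 courses are reported as 4 days with dose intensity 25% too high

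*SAP*

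**What the plan says.** SAP 2.4.1 (Duration of exposure to study treatment) defines exposure to each drug as "Last unit (date/time) of administration of X – First unit (date/time) of administration of X + (1" (the bracket closes after the 1). The added 1 depends on the unit:

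- Date unit: "If the unit is the date, then plus 1".
- Hour unit: "if the unit is the hour, then transfer the exposure duration to days and plus 1 when there are residual hours".

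The document history of the primary-analysis SAP shows which drug the hour unit is meant for: "Update the definition of duration of exposure with consideration of using hours as unit time for rATG". Section 2.4.1 of the final-analysis SAP carries the same rule unchanged. In both SAPs, dose intensity is cumulative dose divided by this duration, and cumulative dose is the sum of all non-zero doses.

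Protocol 6.1.1.2 states that r-ATG "will be administered at a dose of 2.5 to 3.5 mg/Kg/day on Days 1 to 5". Protocol 6.7.2 adds: "Administer the first dose of r-ATG over a minimum of 6 hours; administer doses on subsequent days over at least 4 hours". Protocol 12.3 asks for r-ATG exposure in days, with dose intensity.

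**The concern.** The two branches measure different things. The date branch counts calendar days inclusively, so Day 1 to Day 5 is always 5. The hour branch rounds elapsed time up to whole 24-hour blocks, so its answer depends on what time of day the course began and ended. Two participants who each received five daily infusions can be reported as 5 days and 4 days. Their cumulative doses are the same, so the second also gets a higher dose intensity. This comes from the formula applied to complete data and needs no missing time.

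At stake is the accuracy of two descriptive r-ATG summaries. With about 36 participants, one affected course could set the reported minimum duration or the maximum dose intensity.

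**Working it through.** **Inputs.** Five daily infusions at 2.5 to 3.5 mg/kg/day (Protocol 6.1.1.2). First infusion at least 6 h, later ones at least 4 h (Protocol 6.7.2). Exposure and dose-intensity formulas from SAP 2.4.1. The clock times below are assumptions, because the documents give none. Neither document states an r-ATG duration or dose intensity that could be reproduced.

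**Formulas.**

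- Hour branch: H = last end − first start; days = whole part of H/24, plus 1 if hours remain.
- Date branch: last date − first date + 1.
- Dose intensity (DI) = 5 × daily dose ÷ days.

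**Results.**

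| First start | Last end | H | Hour branch | End-date rule | Start-date rule |
|---|---|---|---|---|---|
| Day 1 09:00 | Day 5 13:00 | 100 h = 4 d 4 h | 5 | 5 | 5 |
| Day 1 12:00 | Day 5 13:00 | 97 h = 4 d 1 h | 5 | 5 | 5 |
| Day 1 13:00 | Day 5 13:00 | 96 h = 4 d 0 h | 4 | 5 | 5 |
| Day 1 14:00 | Day 5 13:00 | 95 h = 3 d 23 h | 4 | 5 | 5 |
| Day 1 20:00 | Day 6 00:30 | 100.5 h = 4 d 4.5 h | 5 | 6 | 5 |

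The first row is the benchmark: an ordinary course gives 5 days under every rule. The last row is a fifth infusion started on Day 5 at 20:00 that runs past midnight.

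**Effect on dose intensity when the result is 4 days.** DI = 5/4 × daily dose, so 2.5 becomes 3.125, 2.8 becomes 3.50, 3.0 becomes 3.75 and 3.5 becomes 4.375 mg/kg/day. DI passes 3.5 once the daily dose is above 3.5 × 4/5 = 2.8 mg/kg. The inflation is also 25% if the unit is mg/day.

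**When it can happen.** The result is 4 days if the Day 5 end time is at or before the Day 1 start time on the clock. The last infusion lasts at least 4 h, so its start must be at least 4 h earlier in the day than the first infusion's start. With a stable daily start time this never occurs.

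**Illustration of frequency (assumed clock times).** Take the Day 5 start as uniform on 08:00–12:00 and its length as uniform on 4–8 h. The end time t (in hours) then has distribution function (t − 12)²/32 for t from 12 to 16. Averaging this over a uniform Day 1 start gives:

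- Start 09:00–13:00: (1³/96)/4 = 0.26%.
- Start 09:00–16:00: (4³/96)/7 = 9.5%.
- Start 10:00–16:00: (4³/96)/6 = 11.1%.

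Of 36 participants, that is between about 0.1 and 4 affected courses.

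**The case against.** Rounding elapsed hours up to days is a definable convention, no stated figure in the plan is wrong, and the hour unit was a deliberate revision. It also has a real advantage: when the last infusion crosses midnight it correctly gives 5 days, where an end-date rule gives 6 and lowers dose intensity by 1/6, about 17%. That advantage stands, and it rules out simply returning to end dates. It does not rescue the 95 h case, which nothing else in either SAP corrects. A reading that keeps fractional days and then adds 1 would give 95/24 + 1 = 4.96 days, but also 100/24 + 1 = 5.17 for an ordinary course. Rounding up is the natural reading.

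Two stronger inferences are tempting, and the documents do not support them.

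- A reader might take the last unit to be the start of the last infusion, which would make 4 days the result whenever the Day 5 start is no later in the day than the Day 1 start. Table 5-2 points the other way, because it handles a missing r-ATG end time: "For rATG end dates only, if partial end time contains no time, then set the time to 00:00". The SAP therefore works with end times.
- A reader might infer that a compliant participant would be reported as over-dosed. No planned output compares dose intensity with the 3.5 mg/kg/day limit, which governs each daily dose. Relative dose intensity was removed from the SAP, all administered doses are listed by subject, and the SAP does not fix mg/kg as the r-ATG dosing unit.

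**Conclusion.** The rule gives a wrong count of treatment days for a definable set of complete courses: 4 days instead of 5, with dose intensity 25% too high. This rests on reading the hour branch as rounding up and on using the end time of the last infusion.

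The frequency cannot be learned from the documents. It is probably low, since it needs a last infusion that starts at least 4 h earlier in the day than the first did. The 0.26% to 11.1% range only shows how strongly the answer depends on assumed clock times, and the upper figures assume a Day 1 start that can be much later than the Day 5 start.

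The consequence is confined to the descriptive r-ATG duration and dose-intensity summaries in the safety set. The primary endpoint is unaffected. The adverse-event observation periods run to 30 days after the last eltrombopag dose, so they do not move. Actual dose intensity has its own denominator and is outside this point. This is a minor correction, worth making because it is easy.

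**What to change.** In section 2.4.1 of both SAPs, replace the hour rule for r-ATG with: last infusion start date minus first infusion start date plus 1. This is consistent with the date rule for the other drugs. In an uninterrupted course it equals the number of distinct infusion start dates.

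The word start matters. End dates, or a count of calendar days on which any infusion was running, give 6 days when the fifth infusion passes midnight. Start dates give 5 days for every complete Day 1–5 course in the table above, and dose intensity then equals the mean daily dose.

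The cost is one sentence per SAP and simpler programming. The default for a missing r-ATG end time would no longer feed this calculation.

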### **Cumulative dose**

Cumulative dose is defined as the total dose given during the study treatment exposure and will be summarized for each of the study treatment components separately.

For patients who did not take any drug the cumulative dose is by definition equal to zero.

The cumulative dose is the sum of the non-zero doses recorded over the dosing period.

### **Dose intensity**

Dose intensity (DI) for patients with non-zero duration of exposure is defined as follows:

DI of X (dosing unit / unit of time) = Cumulative dose of X (dosing unit) / Duration of exposure of X (unit of time).

Actual dose intensity (ADI) for patients with non-zero actual duration of exposure is defined as follows:

ADI of X (dosing unit / unit of time) = Cumulative assigned dose of X (dosing unit) / Actual duration of exposure of X (unit of time).

For patients who did not take any dose of a given drug the ADI is by definition equal to zero.

### **Dose reductions, interruptions or permanent discontinuations**

The number of patients who had dose adjustments, including reductions, increases or interruptions, and the reasons, will be summarized separately for each of the study treatment components.

An interruption is defined as 0 mg dose recorded or absence of record for one or more days. A reduction (increase) is defined as a decrease (increase) in dose from the protocol planned dose or from the previous non-zero dose, even if it has been directly preceded by an interruption. A decrease (increase) in frequency of administration which results in a lower (higher) cumulative dose is also counted as a reduction (increase).

The number of dose adjustments per patient and the corresponding reasons will be summarized.

### **2.4.2 Prior, concomitant and post therapies**

Concomitant therapies will be coded using the WHO Drug Reference List dictionary that employs the WHO Anatomical Therapeutic Chemical (ATC) classification system and summarized by lowest ATC class and preferred term using frequency counts and percentages. Surgical and medical procedures will be coded using MedDRA and summarized by SOC and preferred term. These summaries will include therapies starting on or after the start of study treatment but no later than 30 days after last dose of study treatment or therapies starting prior to the start of study treatment and continuing after the start of study treatment.

All therapies will be listed. Any therapy starting and ending prior to the start of study treatment or starting more than 30 days after the last date of study treatment will be flagged in the listing

as prior or post therapies respectively. Those starting or continuing on or after the start date of study treatment and up to 30 days after the last date of study treatment will be flagged as concomitant therapies in the listing. The safety set will be used for all therapies tables.

## **2.5 Analysis of the primary objective**

The primary objective of the study is to evaluate the efficacy of eltrombopag in combination with r-ATG and CsA in terms of CR rate at Week 26 in the treatment-naïve East-Asian patients with SAA.

### **2.5.1 Primary endpoint**

The primary efficacy endpoint is CR rate at Week 26 (6 months), which is defined as the percentage of all subjects who meet the hematological criteria of CR at Week 26. A complete response (CR) is defined as meeting all the following 3 criteria on 2 consecutive serial blood count measurements at least one week apart but not more than 4 weeks apart.

A CR will be defined as (all 3 must be met):

- Absolute neutrophil count  $> 1.0 \times 10^9/L$
- Platelet count  $> 100 \times 10^9/L$
- Hemoglobin  $> 100 \text{ g/L}$

The primary endpoint will be based on the investigator assessment of response. However, improvement in counts that are dependent upon exogenously administered growth factors or transfusion will not be considered as fulfilling response criteria.

The exclusion period of these therapies are detailed below:

- Platelets transfusions: 7 days preceding the assessment of platelet count
- Packed RBC transfusions: 14 days preceding the assessment of hemoglobin
- Growth factors: 21 days preceding the assessment of response

The analysis of the primary efficacy endpoint will be based on the FAS.

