8.3 Efficacy

Efficacy assessments include hematologic results, transfusion data, assessment of relapse and survival.

Hematologic parameters will be assessed at Screening, weekly from Week 1 to Week 8, then every 2 weeks to Week 26 (weekly until stabilization of the dose), then every 4 weeks until the end of eltrombopag treatment (every 2 weeks until stabilization of the dose) and yearly during the post-treatment follow-up (up to Year 3). Hematologic parameters will also be assessed as per the investigator decision to assess the maintenance of the response, relapse or for safety reasons.

Transfusion data will be recorded for any transfusion administered during the 60 days prior to treatment start and until the end of eltrombopag treatment for all participants who discontinue eltrombopag due to non-response at W26, relapse or alternative SAA treatment, and until the completion of study follow up for all the other participants. The date and time, content and number of units of each transfusion will be recorded.

Relapse will be determined according to the definition in this section by investigator and will be recorded into eCRF.

All participants will be followed for survival status every 3 months regardless of treatment discontinuation reason up to Year 3 until study completion, death, lost to follow-up, or withdrawal of consent for survival follow-up. Survival information can be obtained via phone, and information will be documented in the source documents and relevant eCRFs.

Hematologic response assessment will be performed by investigators at Week 13, Week 26, Week 52 and yearly after. At Week 13 and Week 26, responses assessment needs to be confirmed by two serial blood count measurements performed 1-3 weeks apart.

Response is defined as blood counts no longer meeting the standard ("Camitta") criteria (Camitta et al 1975) for severe pancytopenia in SAA, equivalent to 2 of the following values (Scheinberg et al 2009).

- Absolute neutrophil count $\geq 0.5 \times 10^9/L$
- Platelet count $\geq 20 \times 10^9/L$
- Reticulocyte count $\geq 20 \times 10^9/L$

A CR will be defined as (all 3 must be met):

- Absolute neutrophil count $> 1.0 \times 10^9/L$
- Platelet count $> 100 \times 10^9/L$
- Hemoglobin $> 100 \text{ g/L}$

A PR will be defined as blood counts that do not meet criteria for SAA but are not sufficient for a CR.

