12.4.1 Definition of primary endpoint(s)

The primary efficacy endpoint is CR rate at Week 26 (6 months), which is defined as the percentage of all participants who meet the hematological criteria of CR in [Section 8.3](#) at Week 26. The primary efficacy endpoint will be performed in FAS.

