### **2.5.4 Supplementary analyses**

The CR will also be derived programmatically using laboratory results (criteria details are stated in the [section 2.5.1](#) ) instead of those reported by the investigators in the response assessment CRF. The response will be derived if two consecutive serial blood count measurements meet the defined requirements, where one of the measurements is done at Week 26. The derived

response will be listed against investigator assessment of response and discrepancies will be identified with justifying comment, when available.

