### **Overall response (CR+PR) rate at Week 13, Week 26, Week 52 and yearly after**

Hematologic overall response rate at specific visit is defined as percentage of subjects who achieved hematologic response by investigator assessment at specific visit in FAS.

The overall hematological response is defined as either complete or partial response. CR is defined in [section 2.5.1](#).

Partial response (PR) is defined as blood counts no longer meeting the standard criteria for severe pancytopenia in SAA, equivalent to at least 2 of the 3 criteria below, but are not sufficient for a CR.

- Absolute neutrophil count  $\geq 0.5 \times 10^9/L$
- Platelet count  $\geq 20 \times 10^9/L$
- Reticulocyte count  $\geq 20 \times 10^9/L$

However, improvement in counts that are dependent upon exogenously administered growth factors or transfusion will not be considered as fulfilling response criteria.

The exclusion period of these therapies are detailed below:

- Platelets transfusions: 7 days preceding the assessment of platelet count
- Packed RBC transfusions: 14 days preceding the assessment of hemoglobin
- Growth factors: 21 days preceding the assessment of response.

Of note that the criteria for complete and partial responses must be met on 2 consecutive serial blood count measurements at least one week apart but not more than 4 weeks apart for the Week 13 and Week 26 assessments but only on one blood count measurements for the yearly assessments thereafter.

Patients who relapse or withdraw from the study will be counted and reported as relapsed or withdrawn for all subsequent response assessments. No response (NR) is defined as not fulfilling the response criteria.

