### **Time to response**

Time to response is defined as the time from the date of the start of study treatment until the first documented and confirmed response (either CR or PR) per programmatically derived.

Time to complete response is similarly defined as the time from the date of the start of study treatment until the first documented complete response.

All subjects in the FAS will be included in the time to response/CR calculations.

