# 4 Change to protocol specified analyses

Below-listed endpoints were added to further support efficacy analysis beyond protocol.

- Time to response
- Maximum duration of Platelet and RBC transfusion free

- Proportion of subjects with transfusion decrease
- Changes in platelet count, hemoglobin and neutrophil count

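### The protocol confirms Week 13 and Week 26 responses with counts 1-3 weeks apart; both SAPs allow up to 4 weeks without declaring it, with a direct effect only on the derived Week 26 CR (minor)

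*SAP*

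**What the plan says.** Protocol 12.4.1 defines the primary endpoint as the "percentage of all participants who meet the hematological criteria of CR in" Section 8.3, at Week 26. Section 8.3 sets the confirmation rule: "At Week 13 and Week 26, responses assessment needs to be confirmed by two serial blood count measurements performed 1-3 weeks apart".

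The primary-analysis SAP (2.5.1) requires the three CR criteria to be met "on 2 consecutive serial blood count measurements at least one week apart but not more than 4 weeks apart". Its overall-response text in 2.7.1 repeats the limit for CR and PR: "at least one week apart but not more than 4 weeks apart for the Week 13 and Week 26 assessments". The final-analysis SAP carries the same wording in its own 2.5.1 and 2.7.1.

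Both SAPs state that they are based on protocol version 03, which holds the 1-3 week rule. Section 4 of each, where changes to protocol-specified analyses belong, says "Below-listed endpoints were added to further support efficacy analysis beyond protocol" and lists only added endpoints. The document histories do not mention the interval either.

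Two further statements decide where the difference can act:

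- SAP 2.5.1: "The primary endpoint will be based on the investigator assessment of response". Section 2.7.1 likewise bases the secondary CR rates and the overall response rates on investigator assessment.
- SAP 2.5.4 also derives the Week 26 CR by program from laboratory results, using the 2.5.1 criteria with one of the two counts at Week 26. The derived "response will be listed against investigator assessment of response and discrepancies will be identified with justifying comment".

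**The concern.** Sites were given a 1-3 week rule and the program is given a 1-4 week rule. Two counts 22 to 28 days apart confirm a response under the SAPs but not under the protocol, and nothing tells the reader that the definition moved.

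The derived CR is the planned check on an investigator-assessed primary endpoint in an open-label, single-arm study. If the two sides of the discrepancy listing use different confirmation rules, disagreements caused by the definition are mixed with genuine disagreements about the assessment.

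Time to response runs "until the first documented and confirmed response (either CR or PR) per programmatically derived", and duration of response starts from a confirmed, programmatically derived response. Neither text says which interval makes a response confirmed.

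**Working it through.** **Inputs**

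- Confirmation interval: protocol 8.3, 1-3 weeks = 7-21 days; both SAPs, 1-4 weeks = 7-28 days. Pairs accepted only by the SAPs are those 22-28 days apart.
- Nominal days (protocol Table 8-1): Week 12 = 85, Week 13 = 92, Week 14 = 99, Week 24 = 169, Week 26 = 183, Week 28 = 197. Week 30 = 211 by the same spacing.
- Visit windows (protocol Section 8): Week 13 and Week 26 ±3 days; other visits ±7 days on a stable dose, and ±3 days after a dose modification until the dose is stable.
- Visit spacing after Week 26: at least every 2 weeks until the dose is stable, then every 4 weeks.
- n = 36, exact Clopper-Pearson 95% interval.

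**Step 1. Reproduce the plan's figures.** Lower limit = Beta quantile 0.025 with parameters (x, n − x + 1); upper limit = Beta quantile 0.975 with parameters (x + 1, n − x).

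- 14/36 = 38.9% (23.1, 56.5)
- 16/36 = 44.4% (27.9, 61.9)
- 18/36 = 50.0% (32.9, 67.1), half-width 17.1%

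All match protocol Table 12-2. None depends on the confirmation interval.

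**Step 2. Which visit pairs can be 22-28 days apart?** Gap = nominal difference + (offset of later visit − offset of earlier visit). A ±7 visit paired with a ±3 visit gives 15 × 7 = 105 day combinations; two ±3 visits give 7 × 7 = 49.

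| Pair | Windows | Gap range (days) | Combinations at 22-28 days |
|---|---|---|---|
| Week 24/26 | ±7, ±3 | 4-24 | 6 of 105 |
| Week 24/26 | ±3, ±3 | 8-20 | 0 of 49 |
| Week 26/28 | ±3, ±7 | 4-24 | 6 of 105 |
| Week 26/28 | ±3, ±3 | 8-20 | 0 of 49 |
| Week 26/30 | ±3, ±7 | 18-38 | 46 of 105 |
| Week 12/13 and Week 13/14 | ±7 and ±3 | at most 17 | 0 of 105 each |

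Example, Week 24/26 with ±7: gap = 14 + b − a, and a gap of 22 or more needs b − a ≥ 8. That gives 3 combinations at a = −7, 2 at a = −6 and 1 at a = −5, so 6.

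For Week 26/30, nominally 211 − 183 = 28 days, 10 combinations pass both rules, 46 pass only the SAP rule and 49 fail both. The pair matters only if there is no count between the two visits, because the SAP asks for consecutive counts.

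A missing count opens similar gaps elsewhere: without Week 24, the Week 22/26 pair is nominally 28 days apart (46 of 105). Without Week 12 or Week 14, the Week 10/13 or Week 13/16 pair is nominally 21 days apart (43 of 105).

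These are counts of permitted day combinations, not expected frequencies.

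**Step 3. Size per participant.** 1/36 = 2.8 percentage points. As an illustration with assumed counts, 16/36 = 44.4% (27.9, 61.9) against 15/36 = 41.7% (25.5, 59.2) or 17/36 = 47.2% (30.4, 64.5).

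**The case against.** The textual difference is not in dispute. The case against giving it weight is strong, and much of it stands.

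- **A reader might infer that the SAP has loosened the primary endpoint and so raises the primary CR rate.** The documents do not support that. The primary CR, the secondary CR rates and the overall response rates are all investigator-assessed, and sites worked under protocol 8.3. No change in any of these is shown.
- **The main route needs a departure from the protocol.** A participant whose first CR-level count falls at Week 26 should, under protocol 8.3, have another count within 3 weeks. Because the SAP requires consecutive counts, the program would use that one and not Week 30. The Week 26/30 pair therefore arises mainly where the required confirmation was not obtained in time. Week 30 also lies outside the SAP's Week 26 window (Day 168-196, Table 2-1), and the SAP does not say whether the confirming count may fall outside it. This stands. It makes the route uncommon but does not close it: visits are 4-weekly on a stable dose, and protocol Section 8 anticipates missed visits.
- **Window-edge pairs are few** and vanish with ±3-day windows. They also depend on reading 1-3 weeks as strictly 7-21 days. This stands.
- **The listing already exposes discrepancies**, and with 36 participants the dates can be checked by hand. This stands in part: nothing in the plan asks anyone to separate an interval effect from a disagreement about the assessment.
- **The final analysis is barely touched.** Final-analysis SAP 2.5 and 2.7 do not reproduce the primary-endpoint analyses, the Week 13 CR, the Week 13 and Week 26 overall response rates, or time to response. Only duration of response remains within reach. This stands and limits the remedy.
- **A reader might also infer that time to response and duration of response are certainly affected.** That goes too far; they are affected only if 'confirmed' means the same 7-28 day rule.

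**Conclusion.** The point holds as an undeclared difference between the protocol and both SAPs in the confirmation rule for the Week 13 and Week 26 response. Its severity is minor.

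The direct effect is on the programmatically derived Week 26 CR and on its comparison with the investigator's assessment. The number reclassified cannot be known from the documents and may be 0. At 2.8 points per participant, even one would be visible in the derived rate.

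The conclusion rests on two assumptions: that the program applies the SAP text literally, and that investigators assessed response under protocol 8.3. Confidence is high for the comparison of texts and low for any practical effect.

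**What to change.** **Primary-analysis SAP**

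- In 2.5.1, 2.5.4 and 2.7.1, use the protocol interval of 7-21 days for the Week 13 and Week 26 confirmation. Build the derived Week 26 CR and the discrepancy listing on it.
- Flag any participant confirmed only by a pair 22-28 days apart, and give the 7-28 day rate as a labelled sensitivity result.
- State which interval 'confirmed' uses for time to response and duration of response.
- If 4 weeks is kept, declare it in Section 4 and report both versions.

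**Final-analysis SAP**

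- Align the definition text or declare the difference in Section 4, and state the interval for duration of response.
- The rule in 2.5 against reproducing primary-endpoint analyses needs no exception unless the flag identifies an affected participant.

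**Cost:** a few aligned sentences, a rebuilt listing with one flag, and one sensitivity result. Time to response and duration of response need a re-run only if 'confirmed' used the 7-28 day interval and that is changed. The downside is that the derived CR rate may be slightly lower under 7-21 days; the flag shows by how many participants.
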